#### Diastolic blood pressure

Increase from baseline of  $\geq$  20mm Hg

Post-baseline value > 100mm Hg

Post-baseline value > 100mm Hg and Increase ≥ 20mm Hg

Decrease from Baseline of  $\geq 10 \text{ mm Hg}$ 

Post-baseline value < 50 mm Hg

Post-baseline value < 50 mm Hg and Decrease ≥ 10 mm Hg

• Treatment Compliance: Treatment compliance will be determined for the entire double blind phase. Subjects taking BID or QD dosing will be considered as been compliant. The total tablets taken = total tablets dispensed – total tablets returned.

Compliance = 100 x Total tablets taken / Total tablets Expect

#### Secondary Prevention Risk Scores

The Risk score is calculated by totaling the number of risk factors a subject has at baseline and categorizing the total score into  $0, 1-2, \text{ or } \ge 3$ . See table below.

Risk Factor	Points
Congestive heart failure	1
Hypertension	1
Age ≥ 75 years	1
Diabetes mellitus	1
Prior stroke	1
Prior CABG	1
Peripheral arterial disease	1
Renal dysfunction (eGFR <60 mL/min 1.73 m 	1
Current smoker	1
Prior MI	1

- On treatment: This definition applies to the "On-Treatment" and "On-Treatment plus 30 Days" Analyses Sets described in Section 5.2.1. A subject is considered to be "on treatment" while the subject is on study drug. If a subject permanently discontinues study drug, the subject is considered to be "off treatment". If a subject is taking BID dosing or QD dosing, or stops and restart study drug then the subject is still considered to be "on treatment"
- Subject who Completed the Study on Study Drug: A subject is considered to have completed the study on study drug, if the last dose date for the subject falls 1 day prior or on/after the date of Sponsor notification of Study Completion and "Subject Status at Final Sponsor Notification Visit/Premature Study Discontinuation or "Subject Status at Final 30-Day Follow-up Visit" = "Completed", "Death".
- Subject who Completed the Study: A subject is considered to have completed the study, if in the Final Study Disposition CRF, "Subject Status at Final Sponsor Notification Visit/Premature Study Discontinuation Visit" = "Completed", "Death", or "Subject Status at Final 30 Day Follow-up Visit" = "Completed" or "Death". For these subjects the EOT is the same as the EOS visit.

- Study Completion: Sponsor Notification of Study Completion will occurred once 1401 MACE+ adjudicated events, and 2.5 years median treatment duration.
- Subjects without Any Type of Diabetes at Baseline: Subject must meet the following conditions;
  - o On the Diabetes History Form "Clinical diagnosis of diabetes?" = "No" and
  - o Not initiated any diabetes treatment prior to or at Baseline and
  - o None of the following where available
    - o HbA1c  $\geq$  6.5% in all central or local labs assessments prior to or at Baseline and
    - $\circ$  FPG  $\geq$  126 mg/dL (7.0 mmol/L) in all central or local labs assessments prior to or at Baseline and
    - o 2-hour plasma glucose ≥ 200 mg/dL(11.1mmol/L) by an OGTT test prior to or at Baseline and
    - o random plasma glucose > or = 200 with associated symptoms of hyperglycemia prior to or at Baseline
- Subject who are Pre-diabetic at Baseline: Subject must meet all the following conditions;
  - o On the Diabetes History Form "Clinical diagnosis of diabetes?" = "No" and
  - o Not initiated any diabetes treatment prior to or at Baseline and
  - At least one of the following:
    - o HbA1c 5.7% to <6.5% or
    - FPG 100 to 125 mg/dL (5.55 to 6.94 mmol/L) between Screen and Baseline and
  - None of the following where available
    - o HbA1c  $\geq$  6.5% in all central or local labs assessments prior to or at Baseline and
    - o FPG ≥ 126 mg/dL (7.0 mmol/L) in all central or local labs assessments prior to or at Baseline and
    - o random plasma glucose > or = 200 with associated symptom of hyperglycemia prior to or at Baseline and
    - o 2-hour plasma glucose ≥ 200 mg/dL(11.1mmol/L) by an OGTT test prior to or at Baseline and
- Subject who are Normoglycemic at Baseline: Subject must meet the following conditions:
  - o On the Diabetes History Form "Clinical diagnosis of diabetes?" = "No" AND
  - o Not initiated any diabetes treatment prior to or at Baseline AND
  - o None of the following where available:
    - o HbA1c  $\geq$  5.7% in all central or local labs assessments prior to or at Baseline

- o FPG ≥ 100 mg/dL (5.55 mmol/L) in all central or local labs assessments prior to or at Baseline
- 2-hour plasma glucose ≥ 200 mg/dL(11.1mmol/L) by an OGTT test prior to or at Baseline
- Random glucose > or = 200 with associated symptoms of hyperglycemia prior to or at Baseline
- Subject is not otherwise defined as 'pre-diabetic' at baseline
- Subjects who are T2DM at Baseline: Subject must meet at least one of the following conditions.
  - o On the Diabetes History Form "Clinical diagnosis of diabetes?" = "Yes" and Type of Diabetes = 2 on Diabetic History CRF or
  - o HbA1c  $\geq$  6.5% prior to or at Baseline in either central or local labs or
  - o FPG ≥ 126 mg/dL (7.0 mmol/L) prior to or at Baseline in either central or local labs or
  - o 2-hour plasma glucose  $\geq 200 \text{ mg/dL}(11.1 \text{mmol/L})$  by an OGTT test or
  - Random plasma glucose > or = 200 with associated symptoms of hyperglycemia prior to or at Baseline
  - o Any diabetes treatment prior to or at Baseline
- Subjects who are T1DM at Baseline: Subject must meet the following conditions.
  - On the Diabetes History Form "Clinical diagnosis of diabetes?" = "Yes" and Type of Diabetes = 1 on Diabetic History CRF
- Subjects who are DM at Baseline:
  - o Subjects who meet criteria for T1DM or T2DM above

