9.4.7.2 Prohibited Concomitant Therapies and Drugs

- The following are prohibited as concomitant medications: Other products intended for weight loss including prescription drugs, OTC drugs, and herbal preparations are prohibited as concomitant medications. Any drug that has a risk for serotonin syndrome in its label, or that has been associated with a risk of serotonin syndrome including OTC drugs, should be used only when clearly indicated and within approved dose ranges and durations, as specified in the appropriate labeling. More than 1 additional serotonergic agent is prohibited in combination with lorcaserin HCl (eg an SSRI, antipsychotic and lorcaserin). (revised per Amendment 01)

Serotonergic drugs include, but are not limited to: (revised per Amendment 01)

- a. selective serotonin reuptake inhibitors (SSRIs)
- b. serotonin norepinephrine reuptake inhibitors (SNRIs)
- c. tricyclic antidepressants (TCAs)
- d. bupropion
- e. triptans
- f. St. John's Wort and tryptophan
- g. Monoamine oxidase inhibitors [MAOIs]
- h. linezolid
- i. dextromethorphan

- j. lithium
 - k. tramadol
 - l. antipsychotics or other dopamine antagonists
- If a second nonstudy serotonergic agent is required by the subject during the study, temporarily discontinue study drug and, if possible, wait 3 days after study drug has been discontinued before starting the second serotonergic agent.
 - If the subject discontinues treatment with the 2nd nonstudy serotonergic agent, lorcaserin HCl may be restarted when the 2nd serotonergic agent has been discontinued for at least 15 days, with the following exceptions, which must be discontinued for longer periods of time before restarting study drug.
 - -30 days: fluoxetine, phenelzine, and isocarboxazid;
 - -90 days: the injectable formulation of fluphenazine, haloperidone, paliperidone, and zuclopenthixol.
 - If a subject requires treatment with an agent that has a documented correlation with increased incidence of cardiac valvulopathy and/or PH (eg, pergolide, ergotamine, methysergide, or cabergoline) lorcaserin HCl should be stopped. (revised per Amendment 01) If the subject discontinues treatment with the other agent, lorcaserin HCl may be restarted as long as the other agent has been discontinued for at least 1 month. (revised per Amendment 01)

The following concomitant medication guidelines/restrictions will apply:

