Whenever possible, restart of study drug should be encouraged. Subjects discontinued from study drug due to a serious or severe adverse event considered to be related to study drug by the investigator should not be restarted on study drug. Prior to restarting study drug on subjects who have been discontinued, consideration should be given as to whether the subject has developed any conditions (eg, change in medical status, use of concomitant medications, lack of contraception) exclusionary to taking study drug. See specific instructions in [Section 9.4.5.1](#) for instructions on dosing when restarting study drug and [Section 9.4.7.2](#) for instructions concerning restart of study drug for individuals requiring a second non study drug serotonergic agent. Even if a premature EOT visit was completed due to the discontinuation of study drug, this should not prevent complete study follow-up procedures including the final EoT/Closing Visit, following restart of randomized treatment. (revised per Amendment 01)

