9.7.1.2 Definitions of Analysis Sets

The Safety Analysis Set will be the group of subjects who received at least 1 dose of study drug and had at least 1 postdose safety assessment.

The Intent-to-Treat set (ITT) will be the group of all randomized subjects regardless of whether they took study drug or not.

- Total Time Analysis Set: Using the ITT, events are counted that occur while subjects are on and off treatment. Subjects with no events who discontinue early or complete the study will be censored at their last study contact (see details in the SAP). This will be used for the primary analysis.
- On-Treatment plus 30 Days Analysis Set: Using the ITT, events are counted that occur while subjects are on treatment and up to 30 days from their last dose. Subjects with no events who discontinue early or complete the study will be censored at their last dose day plus 30 days.
- On-Treatment Analysis Set: Using the ITT, events are counted that occur while subjects are on treatment. Subjects with no events who discontinue early or complete the study will be censored at their last dose day.
- Prediabetes Analysis Set: This set includes all subjects in the ITT set without a history of any type of diabetes and who are prediabetic at Baseline. Definition of prediabetes will be found in the SAP. (revised per Amendment 01)
- Nondiabetes Analysis Set: This set includes all subjects in the ITT set without a history of any type of diabetes at Baseline. Definition of nondiabetes will be found in the SAP. (revised per Amendment 01)

T2DM Analysis Set: This set will be all subjects in the ITT who have T2DM at Baseline.

FDA-defined Valvulopathy Analysis Set: This set will be all subjects in the ITT without FDA-defined valvulopathy at Baseline. The data from this study will be pooled with the data from the 3 pivotal lorcaserin HCl studies (APD356-009, -010, and -011).

The PD Analysis Set will be the group of subjects who have both baseline and at least 1 postbaseline assessment of at least 1 PD parameter.

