## 5.2 STUDY SUBJECTS

#### **5.2.1** Definitions of Analysis Sets

The number (percent) of subjects included in each analysis set will be presented by analysis set, treatment group and overall. The description of the analysis data sets are:

- The Safety Analysis Set: will be the group of subjects who received at least one dose of study drug and had at least one post dose safety assessment.
- The Intent-to-Treat (ITT) Set: will be the group of all randomized subjects regardless of whether they took study drug or not. This is the same as the Full Analysis Set.
- Total Time Analysis Set: Using the ITT, events are counted that occur while subjects are on and off treatment. Subjects with no events will be censored at their last study contact or at the visit following Sponsor Notification of Study Completion, whichever

- occurs first. This analysis set will be used for the primary analysis. See Section 8.5 for censoring algorithm.
- On-Treatment plus 30 Days Analysis Set: Using the ITT, events are counted that occur
  while subjects are "on treatment" and up to 30 days from their last dose. Subjects with
  no events who discontinue early or complete the study will be censored at their last dose
  date plus 30 days. See Section 8 for definition of "on treatment" and Section 8.5 for
  censoring algorithm.
- On-Treatment Analysis Set: Using the ITT, events are counted that occur while subjects are "on treatment". Subjects with no events who discontinue early or complete the study will be censored at their last dose date. See Section 8 for definition of "on treatment" and Section 8.5 for censoring algorithm.
- Prediabetes Analysis Set: This set includes all subjects in the ITT set without a history of any type of diabetes and who are prediabetic at Baseline (defined in Section 8).
- Nondiabetes Analysis Set: This set includes all subjects in the ITT set without a history of any type of diabetes at Baseline (defined in Section 8).
- T2DM Analysis Set: This set will be all subjects in the ITT who have T2DM at Baseline (defined in Section 8).
- FDA-defined Valvulopathy Analysis Set: This set will be all subjects in the ITT without FDA- defined valvulopathy at Baseline (defined in Section 8.4). The data from the ECHO sub-study will be pooled with the ECHO data from the 3 pivotal lorcaserin HCl studies (APD356-009, APD356-010, and APD356-011).

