#### 8.5 CENSORING

The individual EOS date will be defined as the time of the last visit or study contact for each individual patient. If no event occurs for an endpoint, the earlier of the last study contact, the visit following Sponsor Notification of Study Completion or death will be treated as the censoring date.

MACE, MACE+ and conversion to T2DM events will be handled in the following manner according to their timing with respect to study milestones:

- Events that are recorded as beginning prior to the date of randomization will not be counted in the event analyses. The subject will be included in the analysis as not experienced the event. These events that are recorded as beginning prior to the date of randomization they will be included in a listing.
- Events that occur at any time after randomization and up to and including the first of the last visit/contact or visit following Sponsor Notification of Study Completion and reported *before* database lock will be adjudicated and included in all efficacy and safety analyses.
- Events that occur at any time after randomization and up to and including the last visit/contact and reported *after* database lock will be not be adjudicated and will not be included in the primary efficacy and safety analysis. They will be recorded in a tabular fashion as part of the final study report and may be included in sensitivity analyses.
- Events that occur after last visit/contact will not be included in the primary efficacy and safety analyses but may be included in the safety database if they fulfill safety reporting criteria.

Events in subjects who withdraw consent for clinical follow-up:

- All events that occur before withdraw of consent are included in analyses.
- Events that occur after withdraw of consent will be included in the primary analyses if they were found through vital status search prior to database lock.

Events in subjects who stop and re-start study medication.

• For the Total Time Analysis Set all events are counted regardless of whether the subject is on or off treatment.

- For the On-treatment Analysis Set events are counted only when the subject in "on-treatment". See Section 8, for definition of "on-treatment".
- For the On-treatment plus 30 days Analysis Set events are counted when the subject is "on-treatment" and up to 30 days from their last dose. See Section 8, for definition of "on-treatment".

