#### 8.5.2 Censoring at Study Completion

8.5.2.1 Censoring for MACE, MACE+, each Component of MACE, and All-Cause Mortality

If non-inferiority between lorcaserin HCl and placebo is confirmed at the interim analysis, then the study will be continued to observe; 1401MACE+ events at approximately 54 months from the start of the study and 2.5 years median treatment duration.

algorithms

MACE non-inferiority and superiority, each component of MACE, and All-cause mortality will analyzed at study completion as part of additional sensitivity analyses. The censoring algorithm is the same for these endpoints but differs by Analysis Set as described in the Table 6, and see Appendix 13.2 for diagrams of censoring algorithms.

For subjects who experienced an event, their time-to-event will be determined from the randomization date (for the Total Time Analysis) and the start date of study drug (for the On-Treatment and On-Treatment + 30-Days Analyses), to the date of the event. The censoring variable will be, CENSORED=0. For subjects who do not experienced an event, the censoring time will be determined from the randomization date (for the Total Time Analysis) and the start date of study drug (for the On-Treatment and On-Treatment + 30-Days Analyses), to the date described in Table 6, along with a matching censoring variable, CENSORED=1.

Table 6 Censoring Date For subjects who did not experienced an event at Study Completion

Table o Ce	ensoring Date For subjects who did not ex	xperienced an event at Study Completion
Analysis		
Set a	Completed the Study	Withdrawal From Study Follow-up
Total Time	In the Final Study Disposition Form use	In the Final Study Disposition Form use the
on Study	the date from , Date of Final Sponsor	date from , Date of Final Sponsor
	Notification/Premature Study	Notification/Premature Study Discontinuation
	Discontinuation	and
	and status is equal to completed	status for discontinuation equals any of the
		following;
		Withdrew Consent
		Lost to Follow up
		Study Terminated by Sponsor
		• death (except for All Cause-mortality)
		• Other
On-	Date of last dose from Study	Date of last dose from Study Medication Form
Treatment +	Medication Form + 30 Days	+ 30 Days
30 Days		
-		
On-	Date of last dose from Study Medication	Date of last dose from Study Medication Form
Treatment	Form	
a See Section	5.2.1 for definitions of Analysis Sets and A	Appendix 13.5.2 for diagrams of censoring

algorithms

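### The SAP counts a drug-free gap as treated time only if study drug is later restarted, which puts an immortal-time type of bias into the on-treatment sensitivity analyses

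*SAP*

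**What the plan says.** **Definition.** SAP Section 8 gives two rules. "If a subject permanently discontinues study drug, the subject is considered to be" off treatment. But a subject on twice-daily or once-daily dosing "or stops and restart study drug then the subject is still considered to be" on treatment. Neither rule limits the length of the gap.

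**Censoring.** In SAP 5.2.1, event-free subjects in the On-Treatment set "will be censored at their last dose date. See Section 8 for definition of" on treatment. Table 6 (SAP 8.5.2.1) gives the operative date as "Date of last dose from Study Medication Form", with 30 days added for the plus 30 Days set.

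**Events.** For subjects who stop and restart, SAP 8.5 says "For the On-treatment Analysis Set events are counted only when the subject in" on treatment, and refers back to Section 8. The plus 30 Days set also counts events up to 30 days after the last dose.

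**Where gaps come from.** Protocol 9.4.7.2 requires a hold when a second serotonergic drug is needed: "lorcaserin HCl may be restarted when the 2nd serotonergic agent has been discontinued for at least 15 days", or 30 or 90 days for named agents. A valvulopathy-linked drug means a hold until it has been stopped for a month. Protocol 9.4.5.1 adds renal and hepatic holds of no fixed length. Protocol 9.5.5.1 states "Whenever possible, restart of study drug should be encouraged", except after a serious or severe adverse event considered related to study drug.

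**Use.** Both sets are sensitivity analyses for MACE, MACE+, T2DM conversion, the MACE+ components and all-cause mortality (SAP 5.4.1 to 5.4.3). The primary analyses use Total Time.

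**The concern.** Whether a given drug-free day is on or off treatment is settled by what the subject does afterwards. Take two subjects who stop drug on the same day. One stays event-free for a year and restarts, so the year enters the denominator. The other dies of an MI at six months. That subject's last dose precedes the gap, so on the natural reading the death is in neither on-treatment set. Restarted gap time therefore carries a survival condition. For death the condition is absolute, because no death can be followed by a restart.

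At stake is how these sets can be read. An on-treatment analysis is usually consulted to see whether off-drug time in a total-time analysis hides an effect. As defined, these sets keep some off-drug time and may lose gap events selectively. SAP 5.4.1.1 even specifies an analysis in these same sets that does not count events during permanent once-daily dosing, yet nothing removes time or events at zero dose.

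**Working it through.** **1. The plan's own figures.** The documents give no figure for gaps. The stated powers reproduce with power = Φ(|ln HR|·√d/2 − 1.96), 1:1 allocation:
- 460 MACE events, HR 1.4: 0.3365 × 10.724 − 1.96 = 1.648, giving 95.0% (stated 95%).
- 1401 MACE+ events, HR 0.85: 0.1625 × 18.715 − 1.96 = 1.08, giving 86.0% (stated >85%).
- 457 conversions, HR 0.75: 0.2877 × 10.689 − 1.96 = 1.115, giving 86.8% (stated 86%).

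The on-treatment definition does not enter these calculations.

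**2. Effect within one arm (natural reading).** Let f be the share of counted time spent in gaps, r the event hazard in a gap relative to on drug, and q the share of gap events after which drug is not resumed. All three are assumed.

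Counted rate / on-drug rate = 1 − f + f·r·(1 − q)

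At r = 1 this is 1 − f·q:
- f = 2%, q = 0.3: 0.994, so 0.6% low.
- f = 5%, q = 0.5: 0.975, so 2.5% low.
- f = 10%, q = 1: 0.900, so 10% low.

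For death in the On-Treatment set q = 1 by construction, so the ratio is 1 − f whatever r is: 0.98, 0.95 and 0.90 for f of 2%, 5% and 10%.

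For other events the sign can change. At f = 5%, q = 0.5, the ratio is 0.975, 1.000 and 1.025 for r of 1, 2 and 3.

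**3. Effect between arms.** The SAP rule was simulated at the protocol's MACE+ rate of 3.5% a year with no treatment effect on drug. Assumptions: 3.5 years of follow-up, 8% a year permanent discontinuation, 120,000 simulated subjects per arm. The comparator is a rule without look-ahead, applied to the same simulated subjects. OT is the On-Treatment set and +30 the plus 30 Days set.

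| Gaps per year (arm A / B) | Mean gap | q | r | SAP OT | SAP +30 | No look-ahead OT | No look-ahead +30 |
|---|---|---|---|---|---|---|---|
| 0.2 / 0.2 | 3 months | 0.5 | 1 | 0.996 | 0.996 | 0.994 | 0.994 |
| 0.3 / 0.1 | 3 months | 0.5 | 1 | 0.980 | 0.987 | 1.002 | 1.002 |
| 0.3 / 0.1 | 3 months | 1 | 1 | 0.970 | 0.984 | 1.009 | 1.011 |
| 0.3 / 0.1 | 6 months | 0.5 | 1 | 0.969 | 0.976 | 0.999 | 1.001 |
| 0.3 / 0.1 | 6 months | 0.5 | 3 | 1.024 | 1.038 | 0.996 | 1.019 |

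The figures carry simulation noise. Dividing the SAP ratio by the look-ahead-free ratio in the same row removes most of it. In the OT set, rows 2 to 4 give 0.980/1.002 = 0.978, 0.970/1.009 = 0.961 and 0.969/0.999 = 0.970. Row 1 gives 1.002 and row 5 gives 1.028. In the +30 set, rows 2 to 4 give 0.985, 0.973 and 0.975, and row 5 gives 1.019.

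**4. Events involved.** In row 1, each 6,000-subject arm has about 25 gap events. About 11 to 12 drop out of OT and about 8 out of +30; the rest are counted. Each arm's OT rate is about 2% low (3.442 against 3.504, and 3.456 against 3.525, per 100 person-years).

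**The case against.** The strongest reply is that losing gap events is an inference. Table 6 covers only subjects without an event and does not say which events count. Section 8 makes a subject off treatment only on permanent discontinuation, so someone who dies during a temporary hold could be read as still on treatment and the death counted. The Appendix 13.2 censoring diagrams, which might settle this, are not shown in the copy reviewed. This stands as a limit on certainty, but it does not rescue the rule. On that reading, events in unresumed gaps are counted while event-free time in unresumed gaps is cut at the last dose, so the rate is biased upwards.

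Four stronger inferences are tempting, and the documents do not support them.
- *That the SAP contradicts the protocol.* Protocol 9.7.1.2 says "Using the ITT, events are counted that occur while subjects are on treatment" but does not define the term, and its single last-dose date also bridges gaps.
- *That the bias favours lorcaserin.* No gap data are given by arm. Related serious or severe adverse events bar restart, and intolerable non-serious ones may be handled by once-daily dosing, which is not a gap. Renal and hepatic holds select sicker subjects, which can reverse the sign.
- *That retained gap time is event-free.* A non-fatal event followed by restart is counted, and the plus 30 Days set keeps events within 30 days of last dose.
- *That a harmful HR would be largely hidden.* Suppose gap shares of 5/3%, 10/5% and 15/8% (lorcaserin/placebo), q of 0.5, 0.8 and 0.8, and the placebo rate during gaps. An on-drug HR of 1.40 then appears as (0.95×1.4 + 0.05×0.5)/(0.97 + 0.03×0.5) = 1.376, and likewise 1.333 and 1.303. With no events lost (q = 0) the same sums give 1.38, 1.36 and 1.34. So about 60–80% of the shift is ordinary off-drug dilution, and nothing in the documents supports gap shares that large.

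**Conclusion.** The concern holds in a limited form. As written, on-treatment status depends on future restart with no gap limit, and either reading of gap events leaves a bias. It is clearest for all-cause mortality and CV death.

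It is confined to the On-Treatment and On-Treatment plus 30 Days sensitivity analyses. A reader might infer that the non-inferiority result is in question. It is not: the interim MACE test and the primary MACE+ test use Total Time, which counts events on and off drug.

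Size and direction are not established. On the natural reading and at equal hazard, assumed gap shares of 2–10% make an arm's rate about 0.6–10% low. The simulated between-arm ratio is 0.97–0.99 under an assumed 3:1 gap imbalance (0.96–0.99 after dividing by the look-ahead-free rule), near 1.00 with equal gaps, and about 1.02 in the On-Treatment set when gap hazard is tripled. Confidence is moderate, because the censoring diagrams were not available.

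**What to change.** In SAP Sections 8 and 8.5, make status depend only on past dosing:
- The subject leaves the On-Treatment risk set at the last dose before any interruption, or 30 days after it in the plus 30 Days set, and re-enters on the restart date. Fit the Cox model with start/stop intervals.
- Apply the same rule whether or not drug is later resumed, and state that events during a hold are classified by it.
- Report gap time and gap events by arm, so that size and direction can be seen.

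The cost is SAP wording and programming. This assumes that interruption and restart dates are held on the Study Medication Form; the SAP names only the last dose date from that form. The sets lose a few events and person-years, and leaving the risk set at a stop caused by illness can still be informative. No treatment rule and no primary analysis changes.
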